2.2 Study Endpoints

The primary safety endpoint is incidence of the composite of infection, secondary procedures to remove the Sensor, or procedure-related adverse events of at least moderate severity.

The primary effectiveness endpoint is time in range, defined as glucose values between 70 mg/dL and 180 mg/dL, at 12 months compared to the first month post-first Sensor insertion.

3 Study Design

Prospective, multi-center study at up to 30 sites in the U.S. enrolling up to 400 adult subjects with diabetes (to insert 273 subjects) including at least 40 subjects ≥ 65 years to achieve at least 1400 Sensor cycles. The subjects will have one Sensor inserted by trained health care professionals approximately every 3 to 6 months dependent upon the Sensor used (90-day Eversense Sensor or 180-day Eversense E3 Sensor).

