3.1 Blinding

There is no blinding in this study.

Statistical Analysis Plan		Page 6 of 11
Sponsor	Study	Version
Senseonics	A Post Approval Study to Evaluate the Long-term Safety and Effectiveness of the Eversense® Continuous Glucose Monitoring (CGM) System	1.0

4 Sample Size Determination

At least 273 enrolled subjects will be inserted with Sensors to achieve at least 1400 Sensor cycles. Subjects will be encouraged to remain in the study up to 27 months of follow-up or after at least 1400 Sensor cycles are completed study wide.

Based on data from the PRECISE (n=81 subjects), PRECISE II (n=90 subjects), PRECISION (n=35 subjects) and PMCF (n=1686 subjects) studies, a total of 31 events occurred that would meet the definition of the primary safety endpoint in this study. With a total of 1892 subjects, this equates to an observed rate of approximately 1.6% with an associated 95% confidence interval of 1.1% to 2.3%. As there is variability associated with this sample, as evidenced by the confidence interval, a conservative expected rate of events for this study is 2.3%. The planned sample size of 1400 total cycles) with this expected rate should provide greater than 95% power for the test of the performance goal of 4%.

Meeting the performance goal of 4% for the planned sample size would require a worst-case observation of a rate of approximately 3% or less (i.e., 41 or fewer events among 1400 cycles). This result will be clinically acceptable and similar to results observed in past studies.

5 Statistical Analyses

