5.6.1.1 Primary Analysis

The primary safety composite endpoint will be evaluated in the following hypothesis, against a Performance Goal of 4%:

H0: The rate of the composite of infection, secondary procedures to remove the Sensor, or procedure-related adverse events of at least moderate severity (p) is greater than or equal to 4%.

$$H0: p \geq 4\%$$

H1: The rate of the composite of infection, secondary procedures to remove the Sensor, or procedure-related adverse events of at least moderate severity (p) is less than 4%.

$$H1: p < 4\%$$

The rate will be tested against the Performance Goal of 4%, using an exact, binomial test, with a one-sided p-value of 0.05 considered evidence of statistical significance. For the primary analysis, data will be analyzed on a per cycle basis, with each cycle contributing an independent observation.

The endpoint will be evaluated using the ITT analysis set.

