5.9 Subgroup Analyses

Subgroup analysis of the primary safety, primary effectiveness, and additional safety endpoints will be performed for the following subgroups: sex, age (Age<median , Age≥median), race (Caucasian vs. non-Caucasian), diabetes type (I vs. II), and sensor life (90-day vs. 180-day). In addition, the rate of procedure-related adverse events will be performed for the subgroup defined by subjects receiving care from a healthcare provide with vs. without an MD degree). These analyses are intended to demonstrate consistency of results across subgroups.

Subgroup analyses will be performed using the primary analysis set. For each subgroup, a regression model will be fit that includes a fixed effect for subgroup. If the p-value for the subgroup term is less than 0.15, additional exploratory analysis may be performed to understand any variations in outcomes by subgroup.

For each subgroup analysis, the summary statistics for each subgroup level will be presented.

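### The Sensor-life subgroup in SAP 5.9 compares 90-day and 180-day Sensors per cycle only, so consistency of the safety composite should also be shown per year of Sensor wear

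*SAP*

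**What the plan says.** SAP 5.9 lists the factors for subgroup analysis of the primary safety endpoint, among them "diabetes type (I vs. II), and sensor life (90-day vs. 180-day"). The method is the same for every factor: "For each subgroup, a regression model will be fit that includes a fixed effect for subgroup". A p-value below 0.15 for that term may lead to further exploratory work. The stated aim is to show consistency across subgroups.

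SAP 5.9 does not give the unit of analysis. For this endpoint SAP 5.6.1.1 does: "data will be analyzed on a per cycle basis, with each cycle contributing an independent observation". Protocol 5.1.1.2 notes that some subjects have both Sensor types, and such subjects can be classified cleanly only cycle by cycle. Per cycle is therefore the natural reading, but it is an inference.

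SAP Section 3 says Sensors are placed "approximately every 3 to 6 months dependent upon the Sensor used". Protocol 6.9 gives the count over 24 months: eight 90-day Sensors or four 180-day Sensors. Under Protocol 6.3.1 adverse events are collected from enrollment to the end of participation, so each wear period is covered in full.

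Neither document plans a wear-time offset, a rate per subject-time or a risk over a common period for this comparison. SAP 5.8 counts subjects with events per interval, but neither by Sensor life nor for the composite.

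**The concern.** For sex, race or diabetes type, the subgroup does not set the length of the observation unit. For Sensor life it does, because cycle length is the subgroup definition. One cycle of either type has one insertion and one removal, but the 180-day cycle has about twice the time in the arm and takes the place of two 90-day cycles.

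The composite mixes components tied to a procedure (secondary removal procedures, procedure-related events) with infection, which can arise during wear. The two types of cycle therefore differ in how much wear-phase risk each can accumulate. A patient on 90-day Sensors in turn goes through twice as many procedures in the same time.

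Protocol Section 2 sets the purpose as safety over up to 27 months of repeated use, which is a question about risk over time. A per-cycle result alone does not answer it for the Sensor-life contrast. Equal risk per year can read as a difference, and a halved risk per year can read as consistency.

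**Working it through.** **The plan's own figure.** SAP Section 4 reports that "a total of 31 events occurred that would meet the definition of the primary safety endpoint in this study", among 1892 subjects. 31/1892 = 1.64%, with exact 95% interval 1.12% to 2.32%, which agrees with the plan. The plan then takes "a conservative expected rate of events for this study is 2.3"%. With 1400 cycles and a 4% goal at one-sided 0.05, the exact limit is 43 events (P(X≤43) = 0.0400; P(X≤44) = 0.0545). Power at 2.3% is 97.4%, so the claim of more than 95% reproduces. The plan's limit of 41 is stricter (P(X≤41) = 0.0203, power 94.7%). The difference does not bear on this point.

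**From per cycle to per unit time.** Let a be the procedural risk per cycle and h the wear-phase risk per 90 days. Assume a constant hazard, the same a and h for both Sensors, and small risks.

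- 90-day cycle: p90 = a + h. 180-day cycle: p180 = a + 2h.
- Per-cycle ratio: R = (a + 2h)/(a + h) = 1 + w, where w = h/(a + h) is the wear-phase share of a 90-day cycle's events.
- Ratio over the same 180 days: (a + 2h)/(2(a + h)) = R/2.

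So R runs from 1 (all risk procedural) to 2 (all risk from wear), while the per-time ratio runs from 0.5 to 1. The documents do not give w.

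**Worked example** (assumed p90 = 2.3%, w = 0.5). p180 = 1.15% + 2 × 1.15% = 3.45%. The per-cycle ratio is 1.5 and the per-time ratio 0.75. Over 720 days the chance of at least one event is 1 − (1 − 0.023)^8 = 17.0% on 90-day Sensors and 1 − (1 − 0.0345)^4 = 13.1% on 180-day Sensors, treating cycles as independent.

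**How often the screen reacts.** Inputs: 1400 independent cycles and 2.3% overall (both from SAP Section 4), and a 180-day share of 15%, 30% or 50%, assumed because the documents give none. The rates solve p90 × (1 − s + R·s) = 2.3% and p180 = R × p90, where s is the share. The test is the likelihood-ratio test of two binomials at 0.15, enumerated exactly. The table gives the probability that the 180-day Sensor is flagged as worse.

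| R per cycle | Wear share w | Ratio per wear-year | s = 15% | s = 30% | s = 50% |
|---|---|---|---|---|---|
| 1 | 0 | 0.50 | 6.9% | 7.3% | 7.4% |
| 1.25 | 0.25 | 0.625 | 16.3% | 20.0% | 20.9% |
| 1.5 | 0.5 | 0.75 | 29.0% | 37.0% | 38.4% |
| 2 | 1 | 1.00 | 56.0% | 68.4% | 68.8% |

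At R = 1 the screen is silent in about 85% of trials, although risk per year of use on the 180-day Sensor is half that on the 90-day Sensor.

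**The case against.** Several counterarguments have force.

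- **Ranking.** A reader might infer that the plan ranks the Sensors and could put them in the wrong order for patients. The documents do not support that. SAP 5.9 checks consistency, a low p-value only permits exploratory work, and no pass or fail result depends on it.
- **The largest figures.** A reader might take 56-69% as the expected size. It belongs to R = 2, which needs every composite event to come from wear. That fits poorly with a composite that is partly procedural. Lower values of R are more plausible, and there the effect is smaller; about 7% is simply the one-sided background of a 0.15 screen.
- **Twice the surveillance.** It is tempting to say that a 180-day cycle is watched twice as long. Only in-situ time doubles, and only nominally. Earlier Sensor sites are re-examined at later visits (Protocol 6.5), the scheduled calls follow each insertion at the same times, and Sensors may be replaced early.
- **Per cycle is legitimate.** It matches the endpoint and the 4% goal, and it answers the question of risk per insertion and removal.
- **An offset is not neutral.** It takes risk as proportional to time. If all risk is procedural, it returns 0.5 purely because there are fewer procedures. Wear-days can also depend on outcome, since infection may lead to removal. In transition subjects, 90-day Sensors always come first, so Sensor type is tied to cycle order.

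All of this stands, and it limits the claim. It does not supply the missing time-based measure. The consistency reading that SAP 5.9 seeks still depends on which scale is used.

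**Conclusion.** The point holds as a cheap improvement to an exploratory analysis. On the per-cycle reading, SAP 5.9 contrasts units that differ about two-fold in wear time and gives no measure per unit of time. For R between 1 and 2, the range produced by any mix of procedural and constant-hazard wear risk, the per-cycle result can point against the 180-day Sensor while risk per year of use is lower on it. The reversal runs in that direction only.

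The probability of flagging the 180-day Sensor as worse is 16-21% at R = 1.25 and 29-38% at R = 1.5. These figures rest on independent cycles, a 2.3% overall rate, an assumed 180-day share of 15-50%, and a wear-phase share that the documents do not give. Neither scale alone is the fair contrast. The primary test and its power are unaffected.

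**What to change.** In SAP 5.9, for the Sensor-life subgroup of the primary safety composite:

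1. State that the cycle is the unit, and keep the per-cycle rate for each Sensor type.
2. Add the event rate per patient-year of Sensor wear for each type, with wear-days counted from insertion to removal. Report the 180-day/90-day rate ratio with its confidence interval from a log-linear model with a log(wear-days) offset. Use GEE or a robust variance clustered by subject, because some subjects contribute both types.
3. Say that consistency by Sensor life will be read on both scales: per cycle for risk per insertion and removal, per wear-year for risk over repeated use. The per-cycle p<0.15 screen should not settle it alone.
4. Note as limitations that Sensor type follows cycle order in transition subjects and that the offset takes risk as proportional to time.

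The cost is a few sentences, one model and one table. The protocol already provides for recording implantation dates (9.5) and each insertion and removal procedure (5.4.2.6 and 5.4.3.3). The downside is a second scale to explain. Fixing both scales in advance also avoids a choice between them after the results of an unblinded study are known.

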Design:	Prospective, multi-center study at up to 30 sites in the U.S. enrolling up to 400 adult subjects with diabetes (to insert 273 subjects) including at least 40 subjects ≥65 years to achieve at least 1400 Sensor cycles. The subjects will have one Sensor inserted by trained health care professionals approximately every 3 to 6 months dependent upon the Sensor used (90-day Eversense Sensor or 180-day Eversense E3 Sensor).
Statistical Analysis and Study Reporting:	Statistical analysis with interim reports will be initiated per FDA PAS guidelines of every 6 months for the first 2 years and annually thereafter. Study hypotheses will be evaluated at end of study

Page 6 of 43

Effective Date:#: 20 March

ABBREVIATIONS

AE Adverse Event
BG Blood Glucose
BMI Body Mass Index

CGM Continuous Glucose Monitoring System

CFR Code of Federal Regulations

Case Report Form CRF DCF **Data Clarification Form Diabetic Keto-Acidosis** DKA **DMS Data Management System DQMP** Data Quality Management Plan eCRF electronic Case Report Form **EDC Electronic Data Capture** ΕN **European Standard** EU **European Union**

FDA Food and Drug Administration

HbA1c Hemoglobin A1c

HCP Health Care Providers (physicians, physician assistants, and/or nurse practitioners)

HHD Hand Held Device

HPA Axis Hypothalamic-Pituitary-Adrenal axis

IRB Institutional Review Board

ISO International Organization for Standardization

ISPAD International Society for Pediatric and Adolescent Diabetes

ITT Intention-to-treat
MMA Mobile Medical App
PAS Post-Approval Study
PMA Premarket Approval

PP Per Protocol
RF Radio Frequency

SAP Statistical Analysis Plan
SAE Serious Adverse Event

SMBG Self-Monitoring Blood Glucose

UADE Unanticipated Adverse Device Effect

Senseonics, Inc. Confidential Information Page 7 of 43
Protocol #: CTP-0034, Version 10 Effective Date:#: 20 March

O TABLE OF CONTENTS

1. IN	TRODUCTION, IDENTIFICATION OF THE DEVICE, AND RATIONA	LE12
1.1.	Names, Intended Use, and Description of Study Device	12
1.1.	1. Description	13
1.1.	2. Calibration	14
1.2.	Summary of Pre-clinical and Clinical Experience	15
2. Pu	rpose of this study	15
3. ST	UDY OBJECTIVES, ENDPOINTS AND HYPOTHESES	15
3.1.	Primary Safety Objective	15
3.2.	Primary Safety Endpoint	16
3.3.	Primary Safety Hypothesis	16
3.4.	Other Safety Endpoints	
3.5.	Effectiveness Objective	16
3.6.	Primary Effectiveness Endpoint	17
3.7.	Other Effectiveness Endpoints	17
3.8.	Patient Perspective Endpoint	17
3.9.	HCP Perspective Endpoint	17

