5.4.2.3. LABORATORY TESTING / BIOMETRICS

Every 6 months (See section 5.3), subjects will have blood samples taken for the following laboratory tests:

HbA1c

Every 6 months (See section 5.3), subjects will have the following biometrics collected:

Senseonics, Inc.
Protocol #: CTP-0034, Version 10

Weight

5.4.2.4. **SENSOR REPLACEMENT**

Insertion of New Sensor

A trained study clinician will insert the new Sensor as described in the Visit 1 section above. Each replacement Sensor will be inserted in the alternate arm.

Removal of Old Sensor

A trained study clinician will remove the old Sensor using appropriate technique described in the Eversense CGM Sensor Insertion and Removal Instructions.

Subjects will be advised that they may take over the counter pain medication if needed for any discomfort after the insertion/removal process. No medication, including medication-containing creams and patches is to be applied over the Sensor insertion/removal sites. Subjects will be advised to keep the areas dry for 24-48 hours. Subjects will be advised to change the dressing approximately 48 hours post insertion, and they will check that the healing process is going as expected (minor redness, no swellings, no increased temperature, no increased pain and no sign of infection). The subjects will be instructed to leave the steri-strips in place until they fall off on their own. If the edges of the strips peel back, they may be trimmed. After 48 hours subjects will be advised to change the dressing as required until the incision is healed. Cleaning can be done with normal saline in the clinic, but at home they can use tap water.

QUESTIONNAIRES 5.4.2.5.

Subjects will be asked to fill out the DDS and CGM satisfaction questionnaires at Visit 3 (Day 180) and 5 (Day 365). HCPs will be asked to fill out a short questionnaire regarding their experience periodically.

5.4.2.6. **DATA COLLECTION**

The HCP performing the Sensor insertion/removal will record information about the insertion/removal procedure on the CRF as appropriate.

5.4.2.7. **ESTIMATED VISIT DURATION**

The total duration of the Follow-up/Sensor replacement visit is approximately 2 hours.

Page 27 of 43

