8.3. OTHER ENDPOINTS

Safety

Other safety endpoints will be summarized using descriptive statistics appropriate to the endpoint being evaluated. There are no formal hypotheses or tests for statistical significance associated with secondary endpoints.

The rates for serious and non-serious adverse events will be summarized as binomial proportions, together with the exact, one-sided upper 95% confidence bound. These will include insertion/removal procedure-related adverse events, and rate of device breakage.

Subgroup analysis of all safety endpoints based on:

- Age (<65 years vs. >65 years, minimum 40 subjects)
- Diabetes type (I vs. II)
- Race (non-Caucasian vs. Caucasian)

Effectiveness

Effectiveness will be measured as percentage change in the percent time in range (based on hours) at one month compared to 12 months using a time in range definition of glucose values between 70 mg/dL and 180 mg/dL. The Time in Range will be summarized as the mean of the subject percentages, together with the median, standard deviation, minimum, maximum, and 25th / 75th percentiles.

Summary statistics will also be provided for the change in HbA1c levels from baseline, and average hours of use per day.

Patient Perspective

Patient satisfaction as measured by validated questionnaires (CGM satisfaction survey and Diabetes Distress Scale) administered at select visits will be reported. The patient questionnaire scores will be summarized as means, median, standard deviation, minimum, maximum, and 25th / 75th percentiles.

Page 39 of 43

Effective Date:#: 20 March

Other Endpoints

Success rates for insertion and removal procedures will be presented to evaluate the

Senseonics, Inc. Confidential Information Protocol #: CTP-0034, Version 10

effectiveness of the training program. Success rate will also be presented based on the HCP experience with insertion and removing Sensors (learning curve by number of cases). It is anticipated that approximately 30% of the insertion and removal procedures will be done by nurse practitioners and physician assistants.

The rates of serious adverse events based on HCP experience with inserting and removing Sensors (learning curve by number of cases) will be examined.

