5.8 Safety Analyses

Adverse events (AE) will be reported for the ITT primary analysis population. AEs will be tabulated with the number of events and subjects with event for each event type and overall. Rates will be reported as the number of subjects who experience at least one event during the analysis interval out of the total number of subjects with follow-up to the beginning of the analysis interval. Serious adverse events will also be tabulated. The rate of all AEs and SAEs reported in the study will be reported.

All AEs and SAEs will also be summarized by relatedness as described above. Adverse events leading to death or study discontinuation will be provided in listing format.

All device deficiencies will be reported in listing format.

Statistical Analysis Plan		Page 11 of 11
Sponsor	Study	Version
Senseonics	A Post Approval Study to Evaluate the Long-term Safety and Effectiveness of the Eversense® Continuous Glucose Monitoring (CGM) System	1.0

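### The MD versus non-MD comparison of procedure-related adverse events is defined by subject, with no rule for subjects treated by both operator types, so it may be diluted or distorted

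*SAP*

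**What the plan says.** SAP 5.9 adds one operator comparison to its list of subgroups: "the rate of procedure-related adverse events will be performed for the subgroup", and the groups are a "subgroup defined by subjects receiving care from a healthcare provide with vs. without an MD degree". For each subgroup, "a regression model will be fit that includes a fixed effect for subgroup", and a p-value below 0.15 may prompt further exploration. The stated purpose is limited: "These analyses are intended to demonstrate consistency of results across subgroups". No margin is given.

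The general rule for adverse events in SAP 5.8 also counts subjects: "Rates will be reported as the number of subjects who experience at least one event during the analysis interval".

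The protocol describes operators by profession and counts their work by procedure. Its abbreviations list defines HCP as "Health Care Providers (physicians, physician assistants, and/or nurse practitioners". Section 8.3 anticipates that "approximately 30% of the insertion and removal procedures will be done by nurse practitioners and physician assistants". Section 5.4.2.4 has a trained study clinician insert and remove Sensors at replacement visits, without requiring the same person or the same profession each time. Section 5.4.2.6 provides for data on each procedure: "The HCP performing the Sensor insertion/removal will record information about the insertion/removal procedure on the CRF as appropriate".

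The other operator analyses (Protocol 8.3, SAP 5.6.5) are procedural success and serious adverse events by number of cases performed. They are not split by operator type.

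**The concern.** A procedure-related event follows a particular insertion or removal by a particular operator. The SAP attaches operator status to the subject instead. A subject with some procedures done by a physician and others by an NP or PA fits both groups, and SAP 5.9 does not say where that subject goes. It also does not say that receiving care from a provider means that the provider performed the procedure. Two analysts could follow the text and produce different tables.

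Two errors become possible. A real operator difference could be diluted, making the p<0.15 prompt less likely to fire. Or, if any non-MD procedure moves a subject into the non-MD group, subjects with more procedures would enter it more often and would also have more chances of an event. A difference could then appear where none exists. This is the only planned analysis that splits safety by operator type, so nothing else would reveal either error.

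**Working it through.** The documents give no power, event count or margin for this comparison, so there is no planned figure to reproduce. The calculations below show the possible size of the problem.

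**Inputs from the documents.** 1400 cycles and 273 subjects (Protocol 8.4.3, SAP 4). NP/PA share of procedures about 30% (Protocol 8.3). Each completed cycle has one insertion and one removal. A full course is eight 90-day or four 180-day Sensors (Protocol 5.3, 6.9).

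**Procedures per subject.** 1400 / 273 = 5.13 cycles, and 2 × 5.13 = 10.3, so about 10 procedures.

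**Share of subjects with both operator types.** If the operator type at each of n occasions is an independent draw with NP/PA probability 0.3, the share is 1 − 0.7^n − 0.3^n.

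- n = 10 procedures: 1 − 0.0282 − 0.000006 = 97%.
- n = 6 visits (five cycles, one clinician doing both procedures at each replacement visit): 1 − 0.1176 − 0.0007 = 88%.
- n = 4 procedures (a subject with two cycles): 1 − 0.2401 − 0.0081 = 75%. Counted as three visits: 1 − 0.343 − 0.027 = 63%.

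With operator type correlated within subject (beta-binomial, 10 procedures), the share is 55% at correlation 0.5, 12% at 0.9, and 0% if each subject keeps one type. The correlation is assumed; the documents do not give it.

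**Dilution.** Assume a true per-cycle risk of 4% for NP/PA and 2% for physicians (ratio 2.0), five cycles per subject and one operator per cycle. Compare the mean per-cycle event rate between the two groups of subjects.

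- Independent operators, subject classified by first operator. The other four cycles average 0.3 × 4% + 0.7 × 2% = 2.6%. Non-MD: (4 + 4 × 2.6)/5 = 2.88%. MD: (2 + 4 × 2.6)/5 = 2.48%. Ratio 1.16.
- Independent operators, any MD cycle puts the subject in the MD group. Non-MD: 4%, but only 0.3^5 = 0.2% of subjects. MD: (2.6% − 0.00243 × 4%)/0.99757 = 2.60%. Ratio 1.54.
- The other two rules tried (any NP/PA cycle; majority of cycles) give 1.36 and 1.33.
- At correlation 0.5 the four rules give 1.54 to 1.65, and at 0.75 they give 1.73 to 1.82. With no mixing the ratio is 2.0.

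**Distortion with no true difference.** Assume 2% risk per cycle for every operator, an independent operator draw at each procedure, half the subjects with 4 cycles and half with 8, and any non-MD procedure placing the subject in the non-MD group.

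- Never non-MD: 0.7^8 = 0.0576 (4 cycles) and 0.7^16 = 0.0033 (8 cycles).
- Risk of at least one event: 1 − 0.98^4 = 7.76% and 1 − 0.98^8 = 14.92%.
- Non-MD group: (0.9424 × 7.76% + 0.9967 × 14.92%)/1.9390 = 11.44%.
- MD group: (0.0576 × 7.76% + 0.0033 × 14.92%)/0.0610 = 8.15%.
- Ratio 11.44/8.15 = 1.40, although operators are identical.

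With 2 versus 8 cycles, as when some subjects withdraw early, the same calculation gives 10.18%/4.11% = 2.48.

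**With procedures as the unit.** 1400 cycles give about 2800 procedures: 0.3 × 2800 = 840 by NPs/PAs and 1960 by physicians, each in exactly one group. Unequal numbers of cycles then enter the denominator and no longer create a difference.

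**The case against.** The case for leaving the text alone is that this is an exploratory subgroup analysis without a hypothesis, added by the SAP; the protocol's own subgroup lists do not include it. If sites mostly use one operator type, almost no subject is mixed and the definition does no harm. That stands: mixing is possible but not established, and the 97% figure needs independent draws at every procedure.

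Three stronger readings are tempting, and the documents do not support them.

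- A reader might infer that the analysis necessarily mixes operators and cannot inform on NP/PA safety. The documents do not say how often operator type changes within a subject, and dilution weakens a contrast without removing it. Nor does SAP 5.9 claim to show equal safety. Without a margin, a per-procedure split would not show it either.
- A reader might infer that this is the test of the training programme for non-physicians. Protocol 8.3 and SAP 5.6.5 give that role to insertion and removal success rates.
- A reader might infer that splitting on the MD degree places some physicians with NPs and PAs. That happens only if some physician operators hold another medical degree, which the documents do not say.

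It is also fair to object that bias toward no difference cannot be taken for granted. The working bears this out: the direction depends on the unstated rule. Finally, Protocol 5.4.2.6 has procedure details recorded only as appropriate, so the availability of an operator-type field needs confirming.

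**Conclusion.** The point holds as a defect of definition. The unit is the subject, the exposure is a procedure repeated about 10 times, the two groups are not mutually exclusive, and no assignment rule is given. The effect on the result is conditional. It is nil if each subject keeps one operator type. With independent operators, an assumed true ratio of 2.0 falls to between 1.16 and 1.54, while a rule based on any non-MD procedure can turn no difference into ratios of 1.40 or 2.48 when cycle counts are unequal. These figures rest on the protocol's 30% share and on assumed risks, correlations and cycle mixes, so they illustrate size and do not predict the result. In every mixed case, events cannot be attributed to the operator who performed the procedure.

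Severity is low. The analysis is exploratory and the primary safety test is unaffected.

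**What to change.** In SAP 5.9, define this subgroup per procedure, by the HCP who performed it: physician versus NP/PA, in line with the protocol's categories. Attribute each procedure-related adverse event to the insertion or removal it followed, use procedures as the denominator, and allow for within-subject correlation, for example with generalized estimating equations, which SAP 5.6.1.2 already plans for the primary endpoint. Keep the purpose as a check of consistency.

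The cost is a revised SAP paragraph and a little more analysis work. Two things need confirming first: that the CRF holds operator type for every procedure, and that events can be linked to a specific one. There is reason to expect both. The learning curves by number of cases already need the operator of each procedure, Protocol 6.1 assesses causality against the insertion or removal procedure, and Protocol 5.4.1.1 and 5.4.2.4 document Sensor location and alternate the arm. If either is missing, the cost rises to a CRF change or retrospective collection from sites.

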8.4. SAMPLE SIZE JUSTIFICATION

8.4.1. PRIMARY SAFETY ENDPOINT:

A total of 1400 Sensor cycles contributing to the analysis is planned.

Based on data from the PRECISE (n=81 subjects), PRECISE II (n=90 subjects), PRECISION (n=35 subjects) and PMCF (n=1686 subjects) studies, a total of 31 events occurred that would meet the definition of the primary safety endpoint in this study. With a total of 1892 subjects, this equates to an observed rate of approximately 1.6% with an associated 95% confidence interval of 1.1% to 2.3%. As there is variability associated with this sample, as evidenced by the confidence interval, a conservative expected rate of events for this study is 2.3%. The planned sample size of 1400 total cycles) with this expected rate should provide greater than 95% power for the test of the performance goal of 4%.

Meeting the performance goal of 4% for the planned sample size would require a worst-case observation of a rate of approximately 3% or less (i.e., 41 or fewer events among 1400 cycles). This result will be clinically acceptable and similar to results observed in past studies.

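### SAP 5.9 aims to demonstrate consistency across subgroups, but its p<0.15 difference screen cannot do so and no between-level estimate with an interval is committed

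*SAP*

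**What the plan says.** SAP 5.9 plans subgroup analyses of the primary safety, primary effectiveness and additional safety endpoints by sex, age (cut at the median), race, diabetes type and Sensor life (90-day or 180-day). A provider-type subgroup is added for procedure-related adverse events only.

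The stated aim is: "These analyses are intended to demonstrate consistency of results across subgroups".

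The method is: "For each subgroup, a regression model will be fit that includes a fixed effect for subgroup". The one decision rule is: "If the p-value for the subgroup term is less than 0.15, additional exploratory analysis may be performed". The other output is: "For each subgroup analysis, the summary statistics for each subgroup level will be presented".

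Section 5.9 gives no consistency margin, no subgroup power, and no commitment to report the difference or ratio between levels with an interval. SAP 5.1.1 allows confidence intervals where appropriate, using the t-distribution for continuous data and Clopper-Pearson for categorical data.

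**The concern.** The aim and the method do not match. A test of difference can give evidence that two levels differ. When it fails to reject, it does not show that they are alike, because the same result arises when there is too little information to tell. Showing similarity needs an estimate of the contrast with an interval, read against a difference that would matter. This holds at any sample size.

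Here the information is also thin: the safety composite is expected in only a few dozen cycles. The named subgroups include the 90-day and 180-day Sensors, which are pooled in one primary rate. A reader told that the study set out to demonstrate consistency, and that nothing was flagged, could take this as evidence that the two Sensors have similar complication rates. The planned analysis cannot support that.

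**Working it through.** **Inputs**
- 1400 cycles (Protocol 8.4.1: "A total of 1400 Sensor cycles contributing to the analysis is planned").
- 31 qualifying events among 1892 earlier subjects, and a planning rate of 2.3% (SAP section 4).
- Each cycle treated as an independent observation (SAP 5.6.1.1).
- Screen at 0.15 (SAP 5.9). Sidedness is not stated; two-sided is assumed, as is usual for a regression term, so the critical value is 1.44.
- Two levels per subgroup. About 50/50 follows for age from the median cut, assuming similar cycles per subject. SAP 5.9 gives no other splits, so uneven splits are assumptions.

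**1. The plan's own figures.** 31/1892 = 1.638%, with a Clopper-Pearson 95% interval of 1.12% to 2.32%, as stated. For the exact one-sided 0.05 test of 4% with n = 1400, P(X≤43) = 0.040 and P(X≤44) = 0.054, so 43 events is the cut-off. Power at 2.3% is P(X≤43) = 97.4%, in line with the stated figure above 95%. (The plan's 41-event limit is stricter than the exact 0.05 cut-off. That is a separate matter.) The plan states no power for the subgroup screen.

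**2. Expected events.** 1400 × 31/1892 = 22.9 and 1400 × 0.023 = 32.2.

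**3. Rates under a doubling.** Let f be the share of cycles in the higher-rate level and p the overall rate, held fixed. The lower rate is r = p/(1+f) and the higher is 2r. With f = 0.5 this gives 1.53% and 3.07% at p = 2.3%, and 1.09% and 2.18% at p = 1.638%.

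**4. Equal split, normal approximation, 700 cycles per level.** z = [r − 1.44·√(2p(1−p)/700)] / √([r(1−r) + 2r(1−2r)]/700).
- p = 2.3%: (0.01533 − 1.44 × 0.00801)/0.00800 = 0.47. Power is 68%, so 32% are missed.
- p = 1.638%: (0.01092 − 1.44 × 0.00679)/0.00678 = 0.17. Power is 57%, so 43% are missed.

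**5. Exact enumeration, likelihood-ratio test.** Probability that a true doubling is not flagged:

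| Share of cycles in the doubled-rate level | 23 events | 32 events |
|---|---|---|
| 50% | 43% | 31% |
| 30% | 43% | 32% |
| 70% | 50% | 40% |
| 25% | 44% | 34% |
| 75% | 55% | 45% |
| 20% | 48% | 39% |
| 80% | 59% | 50% |
| 15% | 53% | 44% |
| 85% | 65% | 57% |

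A Wald test gives the same figures at 50/50 but misses more often when the doubled rate is in the larger level (59% and 45% at a 70% share). The SAP does not say which test is meant.

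**6. What identical observed rates would still allow.** On the log scale, SE = √(1/a − 1/n₁ + 1/b − 1/n₂), where a and b are the events in the two levels.
- 16.1 events in each 700: SE = 0.348, and exp(±1.96 × 0.348) = 0.51 to 1.98.
- 11.5 events in each 700: SE = 0.414, and exp(±1.96 × 0.414) = 0.44 to 2.25.

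So with no observed difference at all, a doubling is only just excluded at 32 events and is not excluded at 23.

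**7. Events needed.** With an equal split, 80% power to flag a doubling needs about 46 expected events. That is more than the 43 with which the primary test can pass at 1400 cycles.

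**The case against.** The strongest reply is that the SAP attaches no conclusion to the screen. A p-value below 0.15 permits further exploration; one above it permits nothing in particular. A reader might infer that the SAP will report every unflagged subgroup as consistent. The documents do not say that, and it would be a forecast of the study report. This part of the reply stands. What remains is that the plan states an aim and supplies no criterion by which it could be met.

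Second, the outputs are not blind to a difference. Level summaries will be shown, the fitted model already estimates the contrast, and SAP 5.1.1 permits intervals. This narrows the gap but does not close it. The intervals are optional, and the categorical method named applies to a single proportion, not to a contrast between two.

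Third, the miss rate depends on the split. A reader might put the headline at half or more by taking 40 of 273 subjects (about 15%) as the older group. That figure is the protocol's minimum for subjects aged 65 or over, whereas SAP 5.9 cuts age at the median. For the age subgroup in the SAP, 31% to 43% is the right range. Higher values belong to assumed splits and depend on which level carries the excess.

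Fourth, 0.15 is already a lenient threshold, and no study decision rests on it. Both are true, and both keep the point minor.

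**Conclusion.** The point holds as a mismatch between a stated aim and the method given for it. A p<0.15 difference screen with level-by-level summaries cannot demonstrate consistency, whatever its power.

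Its size for the primary safety composite is a miss rate for a true doubling of about 31% to 43% at an equal split, and about 32% to 65% by likelihood-ratio test over assumed splits from 70/30 to 85/15. This rests on 1400 independent cycles, 23 to 32 events and a two-sided screen. More events would help: at 41 events the equal-split figure falls to about 23%. Within-subject correlation would generally hurt for subgroups defined by subject: an assumed design effect of 1.2 to 1.4 raises the equal-split figure to about 38% to 53%.

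Two wider readings are not supported. The figures say nothing about time in range, which is continuous and for which no power was worked out; only the argument about aim and method carries over. Nor is the primary conclusion affected, since the 4% test uses all cycles together and does not depend on section 5.9. This is an inexpensive improvement to the plan, not a threat to it.

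**What to change.** In SAP 5.9:
- Change the aim from demonstrating consistency to describing differences in results between subgroups.
- For each subgroup, report the between-level rate ratio or odds ratio (safety endpoints) or mean difference (time in range) with a 95% CI, beside the level summaries.
- State that p≥0.15 will not be reported as evidence of consistency.

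The 0.15 trigger for exploration can stay. The cost is a few sentences and one extra column per subgroup table; no new data are needed, and the fitted models already supply a contrast. What is lost is the consistency claim, which the planned analysis could not support.
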